10.3 Follow-up of SAEs

If information that is not available at the time of the first report becomes available at a later date, the investigator should update the SAE form in the eCRF and provide other written documentation within 24 hours of receipt. However, as a back-up, if required, the SAE paper form should be completed, signed by the investigator, and transmitted within 24 hours to the attention of the contact listed in Section 1.1. Copies of any relevant data from the hospital notes (eg, ECGs, laboratory tests, discharge summary, postmortem results) should be sent to the attention of the contact listed in Section 1.1, if requested.

All SAEs should be followed up until resolution or permanent outcome of the event. The timelines and procedure for follow-up reports are the same as those for the initial report.

10.3.1 Safety Reporting to Investigators, IRBs, and Regulatory Authorities

The sponsor will be responsible for reporting all suspected unexpected serious adverse reactions (SUSARs) and any other applicable SAEs to regulatory authorities, investigators, and IRBs, as applicable, in accordance with national regulations in the countries where the study is conducted. Relative to the first awareness of the event by/or further provision to the sponsor or sponsor's designee, SUSARs will be submitted to the regulatory authorities as expedited report within 7 days for fatal and life-threatening events and 15 days for other serious events, unless otherwise required by national regulations. The sponsor will also prepare an expedited report for other safety issues where these might materially alter the current benefit-risk assessment of an investigational medicinal product or that would be sufficient to consider changes in the investigational medicinal products administration or in the overall conduct of the study. The investigational site also will forward a copy of all expedited reports to his or her IRB in accordance with national regulations.

11.0 STUDY-SPECIFIC COMMITTEES

No independent data safety monitoring board/data monitoring committee is required for this study.

The Takeda clinical science representative and the principal investigator will review the safety and tolerability data and available PK data (if applicable) for each cohort prior to dosing any additional cohort. The decision for the next subsequent dose must be agreed by the Takeda clinical science lead and the principal investigator. If any one person has concerns regarding subsequent dosing then this acts as veto and the decision not to proceed with an additional cohort escalated to Takeda management.

12.0 DATA HANDLING AND RECORDKEEPING

The full details of procedures for data handling will be documented in the Data Management Plan. AEs, PTEs, medical history, and concurrent conditions will be coded using the Medical Dictionary for Regulatory Activities (MedDRA). Drugs will be coded using the World Health Organization Drug Dictionary.

12.1 CRFs (Electronic and Paper)

Completed eCRFs are required for each subject who signs an informed consent.

The sponsor or its designee will supply investigative sites with access to eCRFs. The sponsor will make arrangements to train appropriate site staff in the use of the eCRF. These forms are used to transmit the information collected in the performance of this study to the sponsor and regulatory authorities. eCRFs must be completed in English.

After completion of the entry process, computer logic checks will be run to identify items, such as inconsistent dates, missing data, and questionable values. Queries may be issued by Takeda personnel (or designees) and will be answered by the site.

Corrections to eCRFs are recorded in an audit trail that captures the old information, the new information, identification of the person making the correction, the date the correction was made, and the reason for change.

The principal investigator must review the eCRFs for completeness and accuracy and must sign and date the appropriate eCRFs as indicated. Furthermore, the investigator must retain full responsibility for the accuracy and authenticity of all data entered on the eCRFs.

After the lock of the clinical study database, any change of, modification of, or addition to the data on the eCRFs should be made by the investigator with use of change and modification records of the eCRFs. The principal investigator must review the data change for completeness and accuracy, and must sign and date.

eCRFs will be reviewed for completeness and acceptability at the study site during periodic visits by study monitors. The sponsor or its designee will be permitted to review the subject's medical and hospital records pertinent to the study to ensure accuracy of the eCRFs. The completed eCRFs are the sole property of the sponsor and should not be made available in any form to third parties, except for authorized representatives of appropriate governmental health or regulatory authorities, without written permission of the sponsor.

12.2 Record Retention

The investigator agrees to keep the records stipulated in Section 12.1 and those documents that include (but are not limited to) the study-specific documents, the identification log of all participating subjects, medical records, temporary media such as thermal sensitive paper, source worksheets, all original signed and dated ICFs, subject authorization forms regarding the use of personal health information (if separate from the ICFs), electronic copy of eCRFs, including the audit trail, and detailed records of drug disposition to enable evaluations or audits from regulatory

authorities, the sponsor or its designees. Any source documentation printed on degradable thermal sensitive paper should be photocopied by the site and filed with the original in the subject's chart to ensure long-term legibility. Furthermore, International Conference on Harmonisation (ICH) E6 Section 4.9.5 requires the investigator to retain essential documents specified in ICH E6 (Section 8) until at least 2 years after the last approval of a marketing application for a specified drug indication being investigated or, if an application is not approved, until at least 2 years after the investigation is discontinued and regulatory authorities are notified. In addition, ICH E6 Section 4.9.5 states that the study records should be retained until an amount of time specified by applicable regulatory requirements or for a time specified in the Clinical Study Site Agreement between the investigator and sponsor.

Refer to the phase 1 Site Specifications document for the sponsor's requirements on record retention. The investigator should contact and receive written approval from the sponsor before disposing of any such documents.

13.0 STATISTICAL METHODS

13.1 Statistical and Analytical Plans

A statistical analysis plan (SAP) will be prepared and finalized prior to unblinding of a subject's treatment assignment. This document will provide further details regarding the definition of analysis variables and analysis methodology to address all study objectives.

13.1.1 Analysis Sets

Safety Set

The safety analysis set will consist of all subjects who are enrolled and received 1 dose of study drug. Subjects in this analysis set will be used for demographic, Baseline characteristics, and safety summaries.

PK Set

The PK set will consist of all subjects who receive study drug and have at least 1 measurable plasma concentration or amount of drug in the urine.

If any subjects are found to be noncompliant in dosing schedule or with incomplete data, a decision will be made on a case-by-case basis as to their inclusion in the analysis, but the data will be presented in the subject listings.

PD Set

The PD set will consist of all subjects who receive study drug and have at least 1 postdose PD measurement.

If any subjects are found to be noncompliant in dosing schedule or with incomplete data, a decision will be made on a case-by-case basis as to their inclusion in the analysis but will be presented in the subject listings.

13.1.2 Analysis of Demographics and Other Baseline Characteristics

For each part of the study, descriptive statistics (N, mean, SD, median, minimum, and maximum) will be generated for continuous demographic variables and Baseline characteristics variables (age, height, weight, and BMI) for the pooled placebo group, each TAK-071 dose level, TAK-071 overall, and overall total, as applicable (ie, by sequence and overall only for the cross-over portions of the study, cohorts 16 and 17). For each part, the number and percentage of subjects in each class of the categorical demographic variables and Baseline characteristics variables (sex, ethnicity, and race) will be tabulated for the pooled placebo group, each TAK-071 dose level, TAK-071 overall, and overall total. Placebo data will be pooled across the cohorts within each part.

For each part, demographic variables of screen failure subjects and reasons for screen failures will be summarized overall for subjects who are screened but not enrolled in the study. Individual demographic characteristics, date of informed consent, and reason for screen failure will be listed.

13.1.3 PK Analysis

Plasma and CSF concentrations of TAK-071 and donepezil, where appropriate, will be summarized by dose or regimen over each scheduled sampling time using descriptive statistics (including arithmetic mean, SD, median, minimum and maximum, geometric mean, and percent coefficient of variation of the geometric mean). Individual plasma concentration data vs time will be presented in a data listing, along with graphical plots of individual and mean plasma concentration vs time profiles by treatment.

Plasma PK parameters and CSF PK parameters, where applicable, will be summarized separately for SRD, MRD, presence/absence of donepezil, and for subjects with MCI or mild AD and Japanese subjects. Descriptive statistics (including arithmetic mean, SD, median, minimum and maximum, geometric mean, and percent coefficient of variation of the geometric mean) will be used as appropriate.

Dose proportionality for the SRD and MRD parts (separately) will be assessed using the empirical power law model [25]. This analysis will be carried out to assess the degree of dose proportionality based on the dose proportionality exponent (β) for the model for both C_{\max} and AUC_{∞} on Day 1 and for C_{\max} and AUC_{24} at steady-state.

Dose linearity will be examined in the event that dose proportionality cannot be established by using a simple linear regression on the exposure parameter.

Trough plasma concentrations measured in the MRD part will be summarized to assess steady-state. The time to steady-state will be assessed by fitting trough concentration values to a nonlinear mixed effects model in order to predict the time to achieve 90% of the steady-state trough concentrations separately for each dose.

Time dependency will be investigated in selected MRD cohorts. The time invariance of TAK-071 will be assessed by comparing AUC_{24} for the last day of dosing to the AUC_{∞} for Day 1 using analysis of variance with a random effect for subject and a fixed effect for day. If AUC_{∞} cannot be robustly estimated in a sufficient number of subjects, then the AUC_{last} will be used instead in statistical analyses.

In Cohorts 10 to 12, a linear mixed model will be used to evaluate the effect of TAK-071 on the steady-state PK parameters (C_{\max} and AUC_{24}) of donepezil:

$$y_{ijk} = \mu + \tau_j + \pi_k + s_i + \epsilon_{ijk} \quad (i=1, \dots, N; j=A, B, C; k=1, 2, 3),$$

where μ is a general mean of a logarithmically transformed primary variable, s_i is the random effect of subject i , π_k is the fixed effect of period k , τ_j is the fixed effect of treatment j , ϵ_{ijk} is the random error of the observation y_{ijk} , and N is the number of subjects included in the analysis.

The model will be used to estimate 90% CIs together with their corresponding geometric mean ratios for the PK parameters obtained from the comparisons between the treatments. The comparison of interest is TAK-071 plus donepezil vs donepezil alone.

Other exploratory comparisons, including the PK of Japanese subjects or subjects with MCI or mild AD vs healthy subjects and the effect of donepezil on the PK of TAK-071, will be performed

by using side-by-side tabular summaries of exposure-related PK parameters and by graphical comparisons of concentration-time profiles, as appropriate.

For the BA/FE cohort, PK parameters of TAK-071 will be summarized by regimen. A mixed effects analysis of variance (ANOVA) will be performed on natural logarithms of TAK-071 C_{\max} and AUCs with sequence, period, and regimen as fixed effects and subject nested within sequence as a random effect. Within the framework of ANOVA, comparisons will be performed for tablet versus capsule and for fed versus fasting dosing condition to assess the relative bioavailability of TAK-071.

The ratios and the 90% CIs for the central values of each test regimen relative to the reference regimen will be provided. Wilcoxon signed-rank test will be used to compare t_{\max} between the test and reference regimens.

The concentration and cumulative amounts of TAK-071 excreted in urine will be summarized by dose over each scheduled collection interval and for selected time intervals, ie, 0 to 96 hours postdose, using descriptive statistics for SRD and MRD. Individual urine TAK-071 data vs time will be presented in a data listing, along with plots of individual and mean cumulative amounts excreted in urine vs time profiles will be produced.

A more detailed description of the analyses will be presented in the SAP.

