- To characterize the safety, tolerability, and plasma PK profile of TAK-071 when administered as single and multiple QD oral doses at escalating dose levels in healthy subjects (non-Japanese) in the presence of steady-state exposure of donepezil QD.
- To characterize the safety, tolerability, and plasma PK profile of TAK-071 when administered as single and multiple QD oral doses at escalating dose levels in healthy Japanese subjects.
- To characterize safety, tolerability, and plasma PK profile of 10 mg donepezil when administered as a single dose, and to compare it to combination of 10 mg donepezil plus TAK-071.
- To characterize the safety, tolerability, and plasma PK profile of TAK-071 when administered as multiple QD oral doses to subjects with MCI or mild AD (non-Japanese) receiving donepezil treatment for a minimum of 3 months.

Secondary Objectives:

- To assess safety of 120 mg or higher single dose of TAK-071 measured by EEG.
- To evaluate the urinary clearance of TAK-071 following single and multiple oral doses.
- To evaluate the brain penetration of TAK-071 as measured in CSF following single and multiple dosing.
- To evaluate the dose proportionality and any time dependency in TAK-071 plasma PK.
- To evaluate the effect of multiple daily doses of TAK-071 on donepezil steady-state PK.
- To evaluate the relative bioavailability (BA) of TAK-071 10 mg administered as tablet formulation compared with TAK-071 10 mg administered as DIC formulation.
- To evaluate potential effect of food on the TAK-071 plasma PK following a single oral dose of 10 mg tablet formulation.

Subject Population: Cohorts 1 to 12, 17, and 18 to 22: Healthy non-Japanese subjects aged 18 to 55 years, inclusive. Cohorts 13 to 15: Healthy Japanese subjects aged 20 to 55 years, inclusive. Cohort 16: Subjects aged 55 to 90 years, inclusive, with MCI or mild AD.
	

Number of Subjects: Cohorts 1 to 12, 18, and 19: 8 (6 TAK-071, 2 placebo) Cohorts 13 to 15: 6 (5 TAK-071, 1 placebo) Cohort 16: 8 (minimum of 6 completers) (TAK-071 and placebo) Cohort 17: 12 Cohorts 20 to 22: 12 (6 TAK-071+donepezil, 3 donepezil, 3 placebo) Estimated total: 186 randomized
	
Number of Sites: Estimated total: 1 site in the United States

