6.1.2.3 Japanese Subjects (Cohorts 13 to 15)

The MRD part in Japanese subjects will involve dose escalation through 3 cohorts. Subjects will be confined throughout the Treatment Period from Day -1 to Day 29. Healthy Japanese subjects will be randomized to receive a single dose of TAK-071 or matching placebo in a 5:1 ratio, followed by a 7-day washout period and multiple doses (21 oral doses QD) of TAK-071 or placebo. The 7-day washout period in Cohorts 13 to 15 is intended to provide sufficient time to characterize the TAK-071 terminal disposition phase, but it is not expected to result in complete disappearance of TAK-071 from plasma prior to starting repeat dosing on Day 8. Nonetheless, Day 8 trough concentrations are expected to be very low (ie, <5% steady state C_{max}).

PK parameters will include a determination of time to steady-state, potential for accumulation, and time dependency in PK. In addition, data will be compared with data generated in non-Japanese subjects to determine if there are any ethnic differences in human PK.

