Cohort 13 can start after the last dose of Cohort 7 has been completed, providing there are no safety concerns arising from Cohort 7 following evaluation of the 24-hour postdose blinded safety, tolerability, and available PK data. The oral doses of TAK-071 for Cohorts 13 to 15 will be those used for Cohorts 7 to 9, respectively. This will facilitate a direct comparison of exposure in Japanese and non-Japanese subjects. If TAK-071 is not tolerated at a particular dose level in Japanese subjects, alternative doses may be selected for Cohorts 13 to 15. However, under no circumstances will doses in Japanese subjects exceed those of Cohorts 7 to 9.

Cohort 16, consisting of subjects with MCI or mild AD, may start after Cohorts 10 to 12 have been completed and their preliminary safety, tolerability, and available PK data have been evaluated.

The selected TAK-071 doses in subjects with MCI or mild AD will not exceed the highest TAK-071 dose tested in the healthy subject donepezil combination treatment Cohorts 10 to 12.

The TAK-071 dosing frequency in the healthy subject MRD Cohorts 7 to 15 and patient Cohort 16 will be QD. The dosing duration in all MRD cohorts is planned to be 21 days, as it is expected that the majority subjects will attain steady state prior to the last dosing day. If warranted based on emerging PK data from the SRD (ie, several subjects present $t_{1/2z} > 140$ hours) with acceptable safety and tolerability in preceding cohorts, the duration of TAK-071 dosing may be extended for up to a maximum of 28 days. The maximal duration of dosing in the MRD cohorts of 28 days has been set based on the FDA 'Guidance for Industry - M3(R2) Nonclinical Safety Studies for the Conduct of Human Clinical Trials and Marketing Authorization for Pharmaceuticals' and the available 28-day GLP toxicology studies. Under no circumstances a subject will receive > 28 TAK-071 doses in total through the course of their participation in this study. If the majority of subjects present with shorter $t_{1/2z}$ values (ie, < 65 hours), TAK-071 dosing duration may be shortened to a minimum of 14 days.

Cohort 17, the relative BA and food effect cohorts, a 10 mg single dose will be administered as a DIC or a tablet formulation under fasted condition and tablet formulation in fed state. A dose of 10 mg has been selected because, based on nonclinical and ongoing clinical data, this is the highest anticipated dose likely to be used in future clinical studies.

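### No ratio or confidence interval is planned for the Japanese versus non-Japanese PK comparison, although the planned dose matching would support one

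*Protocol*

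**What the plan says.** Protocol 6.1.2.3 says of the Japanese cohorts that "data will be compared with data generated in non-Japanese subjects to determine if there are any ethnic differences in human PK"; SAP 4.4.3.3 repeats this. Protocol 6.2.2.2 plans the doses to suit: "The oral doses of TAK-071 for Cohorts 13 to 15 will be those used for Cohorts 7 to 9, respectively", with the reason given that "This will facilitate a direct comparison of exposure in Japanese and non-Japanese subjects". The same paragraph makes the matching conditional: if a dose is not tolerated in Japanese subjects, "alternative doses may be selected for Cohorts 13 to 15". Protocol 6.1.2 likewise describes the Japanese doses as no higher than those of Cohorts 7 to 9, and possibly lower.

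Protocol 13.1.3 lists this contrast among the exploratory comparisons and says how it will be done: "by using side-by-side tabular summaries of exposure-related PK parameters", and by plots that set the profiles against each other where appropriate. SAP 7.10.2 summarizes the Japanese and non-Japanese cohorts separately, runs the trough and time-dependency analyses separately, and specifies no estimate that sets one population against the other. Both documents plan ratios with 90% CIs for the donepezil interaction and for the tablet and food comparisons.

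**The concern.** The stated aim is to find out whether exposure differs, and the doses are planned to allow it, but the method stops at description. A reader of the report would see three pairs of geometric means, each from 5 and 6 subjects. Nothing would combine the pairs, and nothing would show what size of difference the data are compatible with. Small per-dose contrasts are easy to over-read when they scatter and to dismiss when they agree.

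Protocol 4.2 expects this part of the study to open global phase 2 and 3 studies to Japanese subjects. The interim analysis in Protocol 13.2.1 is meant to inform phase 2 planning. An estimate with an interval is the natural form for that input.

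**Working it through.** **Planned numbers.** Section 2.0 of the Protocol gives "Cohorts 13 to 15: 6 (5 TAK-071, 1 placebo"), and 6 active with 2 placebo in each of Cohorts 7 to 9.
- Japanese subjects: 3 × (5 + 1) = 18, as in Table 6.a.
- Study total: 64 + 36 + 16 + 8 + 24 + 18 + 8 + 12 = 186, as in Table 6.a.
- Active subjects for this contrast: 3 × 5 = 15 Japanese and 3 × 6 = 18 non-Japanese.

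The plan states no power, precision or margin for this comparison, so there is no such figure to reproduce.

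**Assumption.** The documents give no between-subject CV for Cmax or AUC. I use 20% to 50%, with σ² = ln(1 + CV²). At CV 30%, σ = √ln(1.09) = 0.294.

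**Formulas.** The 90% CI is the estimated ratio times or divided by exp(t × SE), with t the 95th percentile.
- One dose level: SE = σ√(1/5 + 1/6), 9 df, t = 1.83.
- Three matched doses, with dose level and population as fixed effects: SE = σ√[(1/5 + 1/6)/3] = σ√0.1222, df = 33 − 4 = 29, t = 1.70.
- Two matched doses: SE = σ√[(1/5 + 1/6)/2], df = 22 − 3 = 19, t = 1.73.

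**At CV 30%.**
- One dose: SE = 0.178, exp(1.83 × 0.178) = 1.39.
- Three doses: SE = 0.103, exp(1.70 × 0.103) = 1.19.
- Two doses: SE = 0.126, exp(1.73 × 0.126) = 1.24.

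| Assumed CV | One dose (6 vs 5) | Three matched doses (18 vs 15) |
|---|---|---|
| 20% | 1.25 | 1.12 |
| 30% | 1.39 | 1.19 |
| 40% | 1.53 | 1.26 |
| 50% | 1.69 | 1.32 |

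On the log scale the pooled interval is 1.87 times narrower at every CV. With an observed ratio of 1 and CV 30%, it runs from 0.84 to 1.19, against 0.72 to 1.39 for one dose.

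**Which parameters can be pooled.** All six cohorts are sampled to at least 24 h on Day 1 and after the last of the 21 daily doses (Day 21 for Cohorts 7 and 8; Day 28 for Cohorts 9 and 13 to 15). Cmax and AUC24 are therefore available on both occasions.

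Day 1 AUC∞ is different. Protocol Table 9.d samples Cohorts 7 and 8 only to 24 h, while Table 9.e goes to 96 h. Under a one-compartment approximation, the share of AUC∞ beyond 24 h is about exp(−24 ln2/t½). That is 77% at a half-life of 65 h and 89% at 140 h, the two half-lives that Protocol 6.2.2.2 uses as thresholds for changing the dosing duration. Only Cohort 9 and Cohort 15 can be compared on it.

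**Does the extra single dose matter?** Cohorts 13 and 14 receive a single dose a week before daily dosing; Cohorts 7 and 8 do not. With k = ln2/t½ and times in hours, its contribution to last-day exposure is exp(−k·24·27) divided by the sum of exp(−k·24·i) for i = 0 to 20. At a half-life of 140 h this is 0.49%, and it is less at shorter half-lives. It does not block the comparison.

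**The case against.** The best defense is that the plan keeps models for its listed objectives and description for the rest. The donepezil ratio is a secondary endpoint, and tablet bioavailability and food effect are secondary objectives. The Japanese objective is to characterize the PK profile, and no endpoint is a between-population ratio. Protocol 13.3 gives no power basis for these cohorts. The hierarchy is coherent and explains why there is no hypothesis test. It does not explain why an exploratory comparison meant to reveal a difference has no estimate or interval.

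Other parts of the defense stand and limit the point:
- A reader might infer that the data go uncompared, or are compared in tables alone. Protocol 13.1.3 also plans graphical comparison, and SAP 7.1 says the SAP is to be read with the protocol.
- A reader might infer that no difference could ever be bounded. SAP 7.10.2 reports N, geometric means and their %CV, so intervals could be worked out afterwards; what is missing is a prespecified calculation. The SAP also refers to a Clinical Pharmacology Analysis Plan, which is not among these documents.
- A reader might take the matched doses as settled. They are planned, with an explicit exception, and a cohort at an unmatched dose adds nothing to a model with dose as a factor.
- The cohorts are not randomized against each other. The interval would cover sampling error but not other differences between the groups.
- Protocol 13.2.1 and SAP 7.14 unblind these cohorts ahead of Cohort 16. A model added after that would be post hoc.

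**Conclusion.** The point holds as an improvement to an exploratory analysis. The plan sets out to learn whether Japanese and non-Japanese exposure differ and plans matched doses for that purpose, but specifies neither a ratio nor an interval. Pooling over dose would reduce the 90% CI factor at CV 30% from about 1.39 to 1.19, or to 1.24 if only two doses stay matched.

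These figures rest on an assumed CV, on all 33 active subjects being evaluable, on 21 daily doses in each cohort as planned, and on one common ratio across doses.

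A reader might go further and infer that the interval would establish similarity, or would decide whether Japanese subjects can join later studies. The documents do not support that: they define no margin and no decision rule, and Protocol 4.2 also has safety and tolerability in view. Nor does the gap invalidate any listed endpoint.

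**What to change.** Add one paragraph and one table to SAP 7.10.2, labeled exploratory:
- Fit a linear model to ln(Cmax) and ln(AUC24), separately for Day 1 and after the last of the 21 daily doses. Use active subjects only, with dose level and population as fixed effects.
- Report the Japanese/non-Japanese geometric mean ratio with 90% CI, with and without body weight, which is already collected.
- If Japanese doses differ from those of Cohorts 7 to 9, use ln(dose) as a covariate, in line with the power model already planned, or restrict the ratio to the matched dose pairs.
- Do not pool Day 1 AUC∞.
- State that the contrast is non-randomized and is not an equivalence test.
- Keep the tables and plots; they let the reader judge whether a common ratio is reasonable.

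Also correct the time-dependency paragraph of SAP 7.10.2, which labels Cohorts 7 to 9 as Japanese and Cohorts 13 to 15 as non-Japanese. Carried into programming, that swap would invert the ratio.

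The cost is a little more analysis and the common-ratio assumption; no subjects or samples are added. To count as prespecified, the text must be in place before these cohorts are unblinded; if it is added later, it should be reported as post hoc.
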